18	Temperature will be recorded in a diary and recording temperature would be a requirement
19	for study participation.
20	• Duration of ANY of at least three respiratory/systemic symptom of viral illness in days
21	(Symptom 1: fever, Symptom 2: cough, Symptom 3: coryza, Symptom 4: sore throat,
22	Symptom 5: shortness of breath, Symptom 6: chills, Symptom 7: fatigue, Symptom 8: loss
23	of smell or taste, Symptom 9: myalgias, Symptom 10: arthralgias, Symptom 11: headache,
24	Symptom 12: nausea, Symptom 13: vomiting, Symptom 14: diarrhea

1	Confirmation of viral infection based on a FDA approved diagnostic test (for e	xample
2	respiratory panel PCR that also detects RSV and influenza or other respirator	y viruses, rapid
3	antigen test for SARS-CoV-2, PCR for SARS-CoV-2).	
4	• Symptomatic viral infection: proportion of participants with fever, cough, or oth	ner
5	respiratory/systemic symptoms (including but not limited to fatigue, loss of sm	ell or taste,
6	myalgias, arthralgias, shortness of breath, sore throat, headache, chills, coryz	a, nausea,
7	vomiting, diarrhea).	
8	Symptomatic moderate to severe viral infection. Based on established score s	system a viral
9	illness will be categorized as moderate or severe if the participant grades at le	east 2 different
10	symptoms as "moderate" or "severe".	
11	Symptomatic PCR confirmed SARS-CoV-2 infection	
12	Need for oxygen therapy (days)	
13	Hospitalization: Days of hospitalization attributable to viral disease: The media	an number of
14	days (or partial days) spent admitted to an acute care hospital	
15	Respiratory failure requiring ventilatory support attributable to viral disease: T	he median
16	number of days (or partial days) requiring (i) non-invasive or (ii) invasive venti	lation
17	Mortality (proportion of participants who die) attributable to viral disease and a	all-cause
18	mortality	
19		
20		
21	Outcome measures:	
22	Adverse events (day 7, 14): the proportion of participants exhibiting adver	se events of
23	any grade as defined using the established  grading scales for the severi	ty of adverse
24	event, such as the Toxicity Grading Scale for Healthy Adult and Adolesce	nt Volunteers

1	Enrolled in Preventive Vaccine Clinical Trials
2	https://www.fda.gov/media/73679/download).
3	
1	Design of Study:
5	Design of olday.
5	
6	Overview of study design
7	Open label clinical trial (intervention with a diet supplement) to evaluate the safety and efficacy

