8	of treatment with mitoquinone/mitoquinol mesylate (mito-MES) (20 mg daily) daily to prevent
9	any viral infection in high-risk close contacts of cases with possible viral infection.
10	
11	
10	Diagnosis and Kay Subject Selection Criteria (Evolusion and Inclusion).
12	Diagnosis and Key Subject Selection Criteria (Exclusion and inclusion):
13	
14	Inclusion criteria
15	All enrolled participants must meet the following criteria:
16	1. Age 18-65 years old. Rationale: We will recruit 18-65 years old participants to increase
17	feasibility of the study and to ensure the study results are generalizable. Participants older
18	than 65 years old have higher incidence of many comorbidities including kidney, heart and
19	liver disease. It would be important to first document safety in the setting of viral infection in
20	the absence of established kidney, liver and heart disease and other major morbidity.
21	2. Asymptomatic (no symptoms of viral infection) on study entry.
22	3. Exposure to a person with at least two new onset independent symptoms or signs (fever) of
23	respiratory viral disease. Viral infection will be defined clinically based on history obtained by
24	the investigator who is an infectious diseases physician and stringent criteria will be

followed. Viral infection will be defined as presence of at least two new onset independent
symptoms or signs (fever) of respiratory disease that cannot be attributed to bacterial cause.
For example, the combination of coryza (runny nose) and sore throat is very characteristic of
a viral illness since there is no bacterial "rhinitis". The combination of fever and cough is not
specific enough presentation since it can be attributed also to bacterial bronchitis or
pneumonia. A study participant with chronic allergies or chronic sinusitis or asthma will not
be included in the study since they may have chronic runny nose or headache or cough.

8 4. High risk exposure without use of masks to suspected case of viral infection (based

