1 diagnostic test such as SARS-CoV-2 FDA approved test (can delay initiation of treatment for at 2 least 24-48 hours). If a participant has a positive SARS-CoV-2 during the study, then the participant will be allowed to continue the study only if not eligible for another FDA approved 3 treatment for COVID-19, given the potential favorable antiviral and anti-inflammatory effects of 4 5 mito-MES in SARS-CoV-2 infection. However, these participants with a positive SARS-CoV-2 6 test will not be included in the final analysis of this PEP trial. The data obtained from the participants with a positive SARS-CoV-2 test will set the foundation for future studies of use of 7 8 mito-MES as treatment for acute COVID-19. 9 Exclusion criteria for all study participants: 10 11 Participants who meet any of the following criteria at screening will be excluded from the study: 12 1. Use of Coenzyme Q10 or Vitamin E < 120 days from enrollment 13 2. Women with variations in physiological functions due to hormones that may effect immune 14 function and (transgender, **pregnant**, breastfeeding) 3. Pregnant (based on history) or lactating. If the possible study participant is female and 15 sexually active and there is a possibility based on history (timing of most recent sexual 16 17 intercourse and timing of menstrual period) that the possible study participant is pregnant, then the participant will be excluded from the study. Rationale: Additional pregnancy testing 18 will further delay the initiation of treatment and will further compromise feasibility of the study 19

20 given limited resources.

Absence of significant clinical disease clinical diseases [e.g., cardiovascular disease (such as coronary artery/vascular disease, stroke), heart disease (such as congestive heart failure, cardiomyopathy, atrial fibrillation), lung disease (such as chronic obstructive pulmonary disease, asthma, bronchiectasis, pulmonary fibrosis, pleural effusions), kidney disease (glomerular filtration rate or GFR less than 60 ml/min/1.73 m2), liver disease (such as

cirrhosis, hepatitis), cancer, major immunosuppression (such as history of transplantation,

1		HIV infection)] based on history. Rationale: Significant clinical diseases can confound
2		interpretation of results for safety and efficacy (e.g., symptomatic viral infection). For
3		example, a patient with known major lung disease such as chronic obstructive pulmonary

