14	Intervention in adults: Exposure of a potential study participant to a viral infection (whether it
15	was confirmed by an FDA approved diagnostic test or not) in a close contact within the
16	household of the study participant and which may cause severe disease in humans (such as
17	SARS-CoV-2 infection or influenza). Intervention would be 20 mg (4 drug capsules) PO daily
18	initiated within 5 days post exposure and taken daily for up to 14 days.
19	
20	Dose Justification
20	
21	
22	Dose justification
23	In a randomized controlled clinical trial of patients with Hepatitis C (ClinicalTrials.gov Identifier:
24	NCT00433108) mito-MES 40 mg orally daily had anti-inflammatory activity (reduced hepatitis) in

1 an epithelial tissue (liver). Mito-MES is commercially available as a dietary supplement in dose 2 of 10 mg orally daily. The dose of mito-MES that is typically used in clinical trials in humans is 20 mg orally daily. It is likely that a higher dose (40 mg daily) is more effective against SARS-3 CoV-2 infection (better antiviral and anti-inflammatory effects) than the lower dose (20 mg daily). 4 5 Thus, in a proof-of-concept initial study we will test the tolerability and efficacy of the 20 mg 6 dose of mito-MES that can be well tolerated in humans over a period of 14 days (20 mg PO daily). The 80 mg oral dose of mito-MES daily is also well tolerated based on clinical trials in 7 humans but gave higher incidence of gastrointestinal side effects. 8 9 10 Justification of 20 mg dose for penetration in respiratory mucosa. 11

Oral MitoQ can achieve adequate levels in the respiratory mucosa that can inhibit establishment
 of early SARS-CoV-2 infection

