## Main Parameters of Safety

,	•		
۰.	,		
	/		
4	1		

_	
3	Adverse events (day 7, 14): the proportion of participants exhibiting adverse events of
4	any grade as defined using the established  grading scales for the severity of adverse
5	event, such as the Toxicity Grading Scale for Healthy Adult and Adolescent Volunteers
6	Enrolled in Preventive Vaccine Clinical Trials
7	https://www.fda.gov/media/73679/download).
8	
9	Main Parameters of Efficacy
10	
11	Primary measures of efficacy (will be assessed in ALL the study participants):
12	
13	The following primary outcomes are based on criteria that can be obtained reliably and
14	consistently for all the study participants (based on history and thermometer).
15	
16	• Development of any symptom of viral infection within 14 days after exposure (YES/No).
17	• Severity of viral illness based on a quantitative score system. Each of the above 14
18	symptoms will be given a score based on severity: 1 for mild, 2 for moderate, 3 for severe.
19	Then a total severity score will be estimated (range of score is 0-42). Common example: a
20	person with mild coryza, sore throat and cough will be given a score of 3.
21	
22	
23	Secondary measures of efficacy (will be assessed in study participants but some endpoints
24	such as diagnostic tests may not be available in all the study participants):
25	

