#### 13 Assessment of symptom severity of viral infection (including COVID-19(

14

Assessment of symptom severity of viral infection including COVID-19 will be performed based 15 16 on the FDA guidance on Assessing COVID-19-Related Symptoms in Outpatient Adult and Adolescent Subjects in Clinical Trials of Drugs and Biological Products for COVID-1991. Patient-17 reported outcome (PRO) instruments will be used to assess COVID-19-related symptoms. 18 19 PRO assessments of COVID-19-related symptoms will be done at least every 24 hours and will 20 be conducted at the same time each day. Electronic data collection systems will be used with 21 reminders to trial subjects to complete the PRO instrument to minimize missing data and provide time stamps of completion. Alternatively, if a paper-based diary is used, the study team 22 will send reminders (e.g., phone calls, text messages, email) to trial subjects. A set of common 23 24 viral-related symptoms (see Table 1) will be included in the daily PRO assessments of all trial 25 subjects regardless of which symptoms a subject had at baseline, as new symptoms may appear following the baseline assessment. Each symptom will be scored individually using the 26

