## 6 Power/Sample Size:

7

8 The study is purely exploratory and is not powered to do a formal hypothesis testing. The data 9 from this study will set the basis for large randomized controlled clinical trials to test the safety of 10 mito-MES in the setting of treatment of viral illnesses. In addition, preliminary data will be 11 obtained on the efficacy of Mito-MES to reduce severity of viral illness. More specifically, all the proposed primary endpoints of efficacy are based on objective quantifiable criteria (fever based 12 on thermometer, duration of symptoms based on number of days, severity of viral illness based 13 14 on quantitative summary score that considers at least two independent symptoms of viral illness based on a clinically relevant definition of viral illness made by a physician). The "effect size" of 15 16 the intervention Mito-MES on these quantifiable outcomes of viral illness in humans will be 17 determined. The safety of Mito-MES in the setting of viral illness will be recorded. This is essential information for the design of larger RCT studies. 18

19

20 Based on resources, we enrolled 80 study participants.

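### As written, the rule removing SARS-CoV-2-positive participants from the final analysis has no safety exemption, so the adverse-event proportion would omit dosed people known to be infected

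*Combined protocol and SAP*

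**What the plan says.** All references are to the combined protocol and SAP.

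- **Safety aims.** The rationale for the age limit says: "It would be important to first document safety in the setting of viral infection in" people without major organ disease. Power/Sample Size says: "The safety of Mito-MES in the setting of viral illness will be recorded", and calls this essential for designing larger trials. Dose justification adds tolerability: "Thus, in a proof-of-concept initial study we will test the tolerability and efficacy of the 20 mg" dose.
- **Safety measure.** Outcome measures and Main Parameters of Safety define one: "Adverse events (day 7, 14): the proportion of participants exhibiting adverse events of" any grade. No safety analysis set is named.
- **Rule for positives.** The text between the inclusion and exclusion criteria covers participants who test SARS-CoV-2 positive during the study. Such a "participant will be allowed to continue the study only if not eligible for another FDA approved" treatment. It then says that those with a positive "test will not be included in the final analysis of this PEP trial". Their data are kept to inform later treatment studies.
- **Other relevant text.** Retention keeps consenting participants in follow-up for safety and efficacy. Sensitivity analyses names intention-to-treat as primary. Neither says who is in the safety denominator.

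**The concern.** A positive test becomes known after dosing may have begun: participants may start without waiting for a result. Dropping people on that basis means that the adverse-event proportion describes dosed people who were not found to have SARS-CoV-2, rather than dosed people. If adverse events are more frequent in those who test positive, from the infection, the drug or both, the reported figure is too low.

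The removed group also bears directly on a stated aim. Some of them take mito-MES during confirmed infection, which is the setting in which the plan says safety should be documented. Keeping their data for later work does not put them into this trial's safety summary, and no separate summary is defined for them. The rule also sits badly with intention-to-treat as the primary analysis.

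**Working it through.** **1. The plan's own figure.** The sample size of 80 was set by resources. No alpha, power, effect size or event rate stands behind it, so there is nothing to reproduce.

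**2. The texts side by side.**

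| Question | What the plan gives |
|---|---|
| Is safety during viral illness an aim? | Yes (age rationale; Power/Sample Size) |
| Can SARS-CoV-2-positive participants continue? | Yes, if no other approved treatment is open to them |
| Are they in the final analysis? | No, with no exception for safety |
| Is a safety set defined elsewhere? | No |
| Are participants with other or untested viral illness removed? | No |

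**3. Size of the error.** Let n be the number dosed, k the number removed as positive, r₊ the adverse-event rate in those removed and r₀ the rate in those retained.

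- Reported proportion: r₀
- All-dosed proportion: (1 − k/n)·r₀ + (k/n)·r₊
- Understatement: (k/n)·(r₊ − r₀)

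The documents give neither k nor n. At most 80 were dosed, but the schedule of events mentions a mito-MES arm and a drug/no drug row, so n may be smaller. The rates are not given either. Every input below is therefore an assumption, with r₀ fixed at 10%. The cells show the all-dosed proportion; the reported figure is 10% throughout.

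| Fraction removed (k/n) | r₊ = 10% | r₊ = 30% | r₊ = 50% |
|---|---|---|---|
| 10% | 10% | 12% | 14% |
| 20% | 10% | 14% | 18% |
| 30% | 10% | 16% | 22% |
| 40% | 10% | 18% | 26% |

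For r₊ = 30%, the understatement is 0.20 × (30 − 10) = 4 points with 20% removed, and 0.40 × (30 − 10) = 8 points with 40% removed. As a check by counts with n = 80 and k = 16: expected events are 64 × 0.10 = 6.4 among those retained and 16 × 0.30 = 4.8 among those removed, and 11.2/80 = 14%.

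**4. What drives it.** With equal rates the error is zero, whatever the number removed. The difference r₊ − r₀ depends partly on whether viral symptoms are counted as adverse events, which the plan does not say.

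**The case against.** The strongest reply is that a narrower exclusion was meant. The secondary efficacy measures include symptomatic PCR-confirmed SARS-CoV-2 infection, which cannot be reported if every positive is dropped. The Missing data section treats a SARS-CoV-2 death as not creating a missing primary outcome, which presumes that such a person is analysed. Retention promises follow-up for safety. This makes a narrower intent plausible, and it stands as a reason for caution. But no sentence limits the exclusion, so an analyst following the text would drop these people from safety as well.

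Three stronger readings are tempting, and the documents do not support them.

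- *The study will yield no safety data in viral illness.* Participants with other viruses, or with untested clinical illness, stay in the analysis, and the positives' data are retained.
- *The safety figure could be wrong by 10, 25 or 40 points.* If 10%, 25% or 40% of dosed participants are removed, those are the widths of the worst-case interval from x/n to (x + k)/n, where x is the number of events among those retained. An error that large needs a rate of 0% in one group and 100% in the other. It is not an expected error.
- *The plan cannot describe tolerability, because it defines only an any-grade proportion.* A grading scale is cited, and the statistical section promises descriptive safety data. Gastrointestinal items are among the listed symptoms ("Symptom 12: nausea, Symptom 13: vomiting, Symptom 14: diarrhea") and are scored daily ("PRO assessments of COVID-19-related symptoms will be done at least every 24 hours"). Hospitalization and mortality are also collected, although as efficacy measures. Tables by grade, of gastrointestinal events or of stopping, and a rule on whether viral symptoms count as adverse events, are useful reporting detail that analysts can add. Their absence from the text is not an error.

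**Conclusion.** The point holds in limited form and is minor. Read literally, the plan computes its safety proportion after removing dosed participants on a result known only after dosing, and so works against its own aim of recording safety in viral illness. The aim is weakened for SARS-CoV-2 and intact for other or untested illness.

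The size cannot be fixed from the documents. Under assumed adverse-event rates of 30% in positives and 10% in the rest, the understatement is 4 points at 20% removed and 8 points at 40% removed; it is zero if the rates are equal. The conclusion rests on taking the exclusion at its word. If it was meant for efficacy only, the defect is an ambiguity that one sentence would settle. The study is exploratory with no formal testing, so the harm is a potentially misleading descriptive figure passed on to the design of later trials.

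**What to change.** In the text on SARS-CoV-2-positive participants, add that the exclusion does not apply to safety. In Main Parameters of Safety, and in the matching Outcome measures entry, state that adverse events are summarised in all participants who took at least one dose of mito-MES. This should include those later found SARS-CoV-2 positive, whether they continued or had to leave, and the positives should also be shown as a separate row. Keep the any-grade proportion at days 7 and 14 as it is.

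The cost is a few lines of wording and one extra row. The plan already calls for these participants' data to be kept, no outcome is dropped, and the sample size is untouched. There is a small downside. Adverse events in positives will partly reflect COVID-19 symptoms, so the pooled proportion may look less favourable, and attribution to the drug stays limited without a dedicated control group. The separate row lets a reader see that contribution but does not resolve attribution.

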#### 19 **Duration of treatment justification**

The duration of treatment for postexposure prophylaxis will be 14 days. We will use the maximum possible duration of treatment for postexposure prophylaxis so that if we find lack of efficacy in this clinical trial this can be attributed to lack of therapeutic efficacy of the antiviral and not due to suboptimal duration of treatment.

## Main Parameters of Safety

,	•		
۰.	,		
	/		
4	1		

_	
3	Adverse events (day 7, 14): the proportion of participants exhibiting adverse events of
4	any grade as defined using the established  grading scales for the severity of adverse
5	event, such as the Toxicity Grading Scale for Healthy Adult and Adolescent Volunteers
6	Enrolled in Preventive Vaccine Clinical Trials
7	https://www.fda.gov/media/73679/download).
8	
9	Main Parameters of Efficacy
10	
11	Primary measures of efficacy (will be assessed in ALL the study participants):
12	
13	The following primary outcomes are based on criteria that can be obtained reliably and
14	consistently for all the study participants (based on history and thermometer).
15	
16	• Development of any symptom of viral infection within 14 days after exposure (YES/No).
17	• Severity of viral illness based on a quantitative score system. Each of the above 14
18	symptoms will be given a score based on severity: 1 for mild, 2 for moderate, 3 for severe.
19	Then a total severity score will be estimated (range of score is 0-42). Common example: a
20	person with mild coryza, sore throat and cough will be given a score of 3.
21	
22	
23	Secondary measures of efficacy (will be assessed in study participants but some endpoints
24	such as diagnostic tests may not be available in all the study participants):
25	

1 The following secondary outcomes are based on **either non guantitative** criteria (categorical) 2 or criteria that may not be available for all the study participants (for example FDA approved diagnostic tests). The study will not pay for any diagnostic tests. These diagnostic tests for 3 viruses may be available in the setting of real world setting and clinical care of each participant 4 5 (for example if performed by the participant or ordered by a doctor in the setting of clinical care). 6 Development of new onset fever (T> 100.3 F or 38C) based on documented 7 8 measurements of temperature on a daily basis throughout the duration of the study. 9 Temperature will be recorded in a diary and recording temperature would be a requirement 10 for study participation. 11 **Duration** of ANY of at least three respiratory/systemic symptom of viral illness in **days** (Symptom 1: fever, Symptom 2: cough, Symptom 3: coryza, Symptom 4: sore throat, 12 Symptom 5: shortness of breath, Symptom 6: chills, Symptom 7: fatigue, Symptom 8: loss 13 of smell or taste, Symptom 9: myalgias, Symptom 10: arthralgias, Symptom 11: headache, 14 Symptom 12: nausea, Symptom 13: vomiting, Symptom 14: diarrhea 15 Confirmation of viral infection based on a FDA approved diagnostic test (for example 16 17 respiratory panel PCR that also detects RSV and influenza or other respiratory viruses, rapid antigen test for SARS-CoV-2, PCR for SARS-CoV-2). 18 Symptomatic viral infection: proportion of participants with fever, cough, or other 19 20 respiratory/systemic symptoms (including but not limited to fatigue, loss of smell or taste, 21 myalgias, arthralgias, shortness of breath, sore throat, headache, chills, coryza, nausea, 22 vomiting, diarrhea). 23 Symptomatic moderate to severe viral infection. Based on established score system a viral illness will be categorized as moderate or severe if the participant grades at least 2 different 24 25 symptoms as "moderate" or "severe".

- Symptomatic PCR confirmed SARS-CoV-2 infection
- 2 Need for oxygen therapy (days)
- Hospitalization: Days of hospitalization attributable to viral disease: The median number of
   days (or partial days) spent admitted to an acute care hospital
- Respiratory failure requiring ventilatory support attributable to viral disease: The median
   number of days (or partial days) requiring (i) non-invasive or (ii) invasive ventilation
- Mortality (proportion of participants who die) attributable to viral disease and all-cause
   mortality
- 9
- 10 **3.12 Experimental protocol of study**
- 11

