## 3 DATA AND SAFETY MONITORING PLAN

4

a) Medical Supervision and Subject Surveillance. [name], board certified
internist and infectious diseases/HIV specialists, will serve as the Physicians of Record for the
study and has extensive experience with clinical oversight of such trials. [name] will make
final decisions regarding subject screening/enrollment and monitor/oversee clinical status and
subject safety. All of the screening data and information collected throughout the study will be
evaluated by [name].

11 b) Data Safety Monitoring Plan. To ensure the safety of subjects, they will need to meet 12 rigorous inclusion/ exclusion criteria, including comprehensive health screening procedures. The participants' personal physicians will also be informed of their patients' participation in the study. 13 14 Supervising Physician. The local investigator ([name]) will have access to all data related to 15 safety assessments. Safety will be monitored via questionnaire. Safety assessments will be performed at study visits. At the screening visit, after review of eligibility, subjects will provide a 16 17 detailed clinical history (including smoking, alcohol and medication history). Subjects will then 18 undergo a full clinical systems review.

19

The local investigator ([name]) will be available to provide direct evaluation of any clinicallyrelated concerns that might arise during the study. The principal investigator ([name]) will directly discuss with the members of UCLA IRB any concerns for adverse events and make recommendations for continuing or stopping the study. Given published safety data of Mito-MES we do not anticipate any major clinical side effects related to safety of Mito-MES especially since every effort will be made to minimize any potential side effects such as nausea

1	(administration of <80 mg of Mito-MES, administration with a full stomach, exclusion of
2	participants with known gastrointestinal disease that may predispose them to nausea).

- 3
- 4

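### Gastrointestinal upset, the drug effect the plan expects, can count as viral illness on the literal endpoint wording, and adverse events are not separated from symptoms of the illness

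*Combined protocol and SAP*

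**What the plan says.** **Efficacy.** Main Parameters of Efficacy gives two primary outcomes. The first is "Development of any symptom of viral infection within 14 days after exposure (YES/No". The second is a severity score that sums 14 symptoms, each graded 1 to 3: "Then a total severity score will be estimated (range of score is 0-42". The symptom list, printed with the secondary outcomes, closes with "Symptom 12: nausea, Symptom 13: vomiting, Symptom 14: diarrhea". Two further secondary outcomes use these items:

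- "Symptomatic viral infection: proportion of participants with fever, cough, or other" respiratory or systemic symptoms, with nausea, vomiting and diarrhea named among them.
- The moderate-to-severe category, under which an "illness will be categorized as moderate or severe if the participant grades at least 2 different" symptoms as moderate or severe.

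**Case definition.** Under Objectives, viral infection is a clinical diagnosis by the investigator. It needs two or more new symptoms or signs of respiratory disease not attributable to a bacterial cause. Power/Sample Size describes the severity score as resting on two or more independent symptoms and a physician's definition of viral illness.

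**Drug toxicity.** Dose justification says the 80 mg dose was well tolerated in "humans but gave higher incidence of gastrointestinal side effects". The Data and Safety Monitoring Plan says "every effort will be made to minimize any potential side effects such as nausea". People with GI disease that predisposes to nausea are excluded, and the capsules are taken with food.

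**Safety.** The outcome is "Adverse events (day 7, 14): the proportion of participants exhibiting adverse events of" any grade.

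**The concern.** One diary entry can serve as an efficacy failure, as an adverse event, or as both, and the plan gives no rule for choosing. Attribution to viral disease is specified for hospitalization, ventilatory support and death, but never for symptoms.

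Timing does not separate the two sources either. Participants enter without symptoms, take the drug for up to 14 days, and are assessed for symptoms within 14 days after exposure.

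Two stated aims are affected. The duration-of-treatment justification wants a negative result to be attributable to lack of antiviral effect; intolerance counted as illness is a rival explanation. Power/Sample Size presents the effect size and the safety record as the basis for larger trials, and each would carry some of the other's signal.

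**Working it through.** **1. Score range, reproduced.** 14 symptoms × 3 points = 42, as stated.

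**2. Weight of the GI items.** 3 × 3 = 9 points; 9/42 = 21.4%. Without them the range is 0 to 42 − 9 = 33. The diary instrument in Table 1 scores smell and taste separately at 0–2 and has no separate arthralgia item. Its maximum is 10×3 + 2×3 + 2×2 = 40, so the GI share there is 9/40 = 22.5% and 31 points remain.

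**3. What GI symptoms alone can trigger, taking each rule literally.**

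| Outcome | GI symptoms alone sufficient? |
|---|---|
| Any symptom of viral infection (primary) | Yes, one item |
| Symptomatic viral infection | Yes, one item |
| Severity score (primary) | Yes, unless a respiratory illness is presupposed |
| Moderate to severe | Two GI items graded moderate meet the count; whether a respiratory illness is required is not said |
| Duration | Only if all three GI items occur (needs at least three symptoms) |
| Fever, test confirmation, oxygen, hospitalization, ventilation, death | No |

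Two GI items graded moderate score 2 + 2 = 4. The plan's own common example of a viral illness (mild coryza, sore throat and cough) scores 3.

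**4. Added cases.** Let v be the proportion with genuine viral symptoms and g the proportion with drug-caused GI symptoms, taken as independent. The plan gives neither. Its only related figure is under 5% attrition from GI discomfort at 40 mg/day, which is not a symptom rate and not the trial dose. If all 80 took the drug:

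- added cases = 80 × g × (1 − v)
- observed any-symptom rate p = 1 − (1 − v)(1 − g)
- GI-only share of cases = g(1 − v)/p
- if every illness symptom is also recorded as an adverse event and there are no other events, the share of participants with any event who have a drug-caused GI event = g/p

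| v (assumed) | g (assumed) | Added cases | p | GI-only share of cases | Drug GI share of those with any adverse event |
|---|---|---|---|---|---|
| 20% | 5% | 3.2 | 24% | 17% | 21% |
| 20% | 10% | 6.4 | 28% | 29% | 36% |
| 40% | 5% | 2.4 | 43% | 7% | 12% |
| 40% | 10% | 4.8 | 46% | 13% | 22% |

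At v = 10% the GI-only share is 31% (g = 5%) to 47% (g = 10%). A low v is possible, because participants who test positive for SARS-CoV-2 are left out of the final analysis.

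**5. Effect on a comparison, if one is made.** Suppose the true risk falls from 40% untreated to 20% on drug (relative risk 0.50) and GI effects arise only on drug. At g = 5% the observed risk on drug is 1 − 0.80 × 0.95 = 24%, and 24/40 = 0.60. At g = 10% it is 1 − 0.80 × 0.90 = 28%, and 28/40 = 0.70. The bias is against the drug.

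**The case against.** The strongest reply is that the outcomes presuppose a physician-defined respiratory illness. The Summary states the primary measure as development of viral illness, the Objectives define viral infection by respiratory symptoms, Power/Sample Size ties the score to that kind of definition, and the moderate-to-severe rule grades a viral illness. On this reading a participant with nausea and diarrhea alone is neither a case nor graded. For the score and the moderate-to-severe category the reading is available. A reader might infer that such a participant must be recorded as a moderate-to-severe viral infection, and the documents do not establish that. The reading does not rescue the first primary outcome or *symptomatic viral infection*, whose wording admits GI-only cases.

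Other points that stand:

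- Only nausea is named individually as a drug effect. Vomiting and diarrhea are inferred from the general phrase. The higher incidence was reported at 80 mg; this trial uses 20 mg, with food, and excludes people prone to nausea. The true g may be low.
- A reader might infer that every viral symptom is an adverse event by definition. The plan does not say so; the inference rests on the absence of any exception, and the cited grading scale is not reproduced.
- Multiplying 80 by 5–10% to get 4 to 8 false cases ignores participants who are also virally ill. It also assumes that all 80 took the drug, while the eligibility text and schedule of events mention compared groups and a no-drug condition.
- The study is descriptive, without formal hypothesis testing.

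**Conclusion.** The concern holds as a defect in endpoint wording that contaminates both results. On the literal text, GI intolerance can be counted as viral illness in one primary and one secondary outcome, in conflict with the plan's own respiratory definition. The moderate-to-severe rule is ambiguous, and the any-grade adverse-event proportion mixes illness with drug effect.

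A reader might go further and conclude that neither efficacy nor safety can be interpreted. The documents do not support that: 33 of 42 score points are not GI items, several secondary outcomes contain none, and symptoms are scored individually each day, so GI-free versions can be derived.

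The size is about 2.4 to 6.4 added cases, assuming v of 20–40%, g of 5–10%, independence, and all 80 on drug. It shrinks if fewer took the drug or if GI effects at 20 mg are rarer, and matters most if viral illness is uncommon. The safety proportion is the weaker of the two results: under the same assumptions, and if illness symptoms are recorded as adverse events, only 12–36% of participants with any event would have a drug-caused GI event.

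**What to change.** 1. **Efficacy.** Reconcile the any-symptom, *symptomatic viral infection* and moderate-to-severe outcomes with the case definition under Objectives, so that GI symptoms alone do not make a viral case. Report the severity score with and without items 12–14 (0–42 and 0–33; if Table 1 is the scoring instrument, 0–40 and 0–31). Because 80 participants are already enrolled, label this as a post-enrolment change if it is made after data were seen.
2. **Safety.** Tabulate adverse events by symptom, with GI events shown separately and their onset given relative to first dose. Give the overall proportion with and without events that fall inside a study-defined viral illness. State that this split describes timing and does not prove cause, since drug-related nausea can occur during a cold.

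**Cost.** Endpoint and table wording only. The Table 1 items stay as they are, and the daily symptom and adherence diaries already hold what is needed. The downside is that a purely GI viral illness would not count as an efficacy failure, which already matches the plan's respiratory definition.
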